6.6. Time to Study Treatment Discontinuation

This only includes the belimumab study medication as prescribed in Year 1 (and Year 2 for Arms C) i.e. this does not include re-start belimumab for subjects in Arms A&B in Year 2.

Year 1 (all arms) and Year 1&2 for Arms A&B only

- If the last dose of belimumab+10 days is prior to the Week 52 visit date (where Week 52 visit date is as observed, or predicted as day1+364 for subjects who do not have a Week 52 visit) then the subject has discontinued treatment (had the event / CENSOR=NO=0) at the earliest non-missing date of (last dose date +7, date of death, withdrawal date, LTFU date)
- If the last dose of belimumab + 10 days is on or post the Week 52 visit date (where Week 52 visit date is as observed, or predicted as day1+364 for subjects who do not have a Week 52 visit) then the subject has a censored time to discontinued treatment (does not have the event / CENSOR=Yes=1) at the earliest non-missing date of (observed or predicted Week 52 visit date, death date, withdrawal date, LTFU date)

Year 1&2 for arm C only

- If the last dose of belimumab + 10 days is prior to the Week 104 visit date (where Week 104 visit date is as observed, or predicted as day1+728 for subjects who do not have a Week 104 visit) then the subject has discontinued treatment (had the event / CENSOR=NO=0) at the earliest non-missing date of (last dose date +7, date of death, withdrawal date, LTFU date)
- If the last dose of belimumab + 10 days is on or post the Week 104 visit date (where Week 104 visit date is as observed, or predicted as day1+728 for subjects who do not have a Week 104 visit) then the subject has a censored time to discontinued treatment (does not have the event / CENSOR=Yes=1) at the earliest non-missing date of (observed or predicted Week 104 visit date, death date, withdrawal date, LTFU date)

A KM plot of time to belimumab treatment discontinuation will also be generated [F11.02]. The figures will be repeated for the Week 104 reporting with all data from Year 1 and 2 combined [F21.02]. Due to the design of the study Arms A & B will be truncated at the end of Year 1. A listing of subjects who discontinued belimumab or Rituximab treatment, including reason will be produced [L11.04, L11.05 , L21.03].

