Randomization and the first dose of belimumab should be completed within 35 days of initiation of screening procedures. Participants will be receiving stable standard therapy at entry. At randomization, participants will be stratified by their screening SLEDAI-2K score (≤9 vs. ≥10), by immunosuppressant use at screening (immunosuppressant use vs. no use) and by screening corticosteroid dose (prednisone equivalent ≤10 mg/day vs. >10 mg/day). Belimumab will be administered SC on Day 1 and then weekly (i.e., every 7 days ±1 day) through Week 51 for Arms A and B, and through Week 103 for Arm C. SC injections will be administered at alternating injection sites between the left or right thighs and the abdomen. Rituximab-placebo or rituximab will be administered by intravenous (IV) infusions at Weeks 4 and 6 for Arms A and B. Participants in Arms A and B will be administered a pre-medication regimen 30 minutes before each rituximab-placebo or rituximab infusion on Weeks 4 and 6, including methylprednisolone 100 mg IV or equivalent, an antihistamine, and acetaminophen or equivalent.

Participants in any arm who are deemed treatment failures for efficacy endpoints at any time during the study will be encouraged to remain in the study and continue to have all efficacy and safety assessments.

Participants randomized to Arms A or B who enter the study on immunosuppressants will discontinue immunosuppressants prior to or on the day of the Week 4 visit. Continuing the stable immunosuppressant dose until Week 4 allows participants to receive 3 weeks of belimumab SC prior to discontinuing their immunosuppressants. Corticosteroids may be adjusted as necessary during this transition period. If participants in Arms A and B receive immunosuppressants after the Week 4 visit they will be deemed treatment failures. Participants in Arm C will continue their stable immunosuppressants throughout the study at the discretion of the investigator. If participants in Arm C require an increased dose of their stable immunosuppressant after Week 12 or addition of a new immunosuppressant they will be considered a treatment failure.

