- a. Starting at Week 4 and throughout the study period including follow-up, a study visit time window ± 7 days is acceptable. Note: Every effort should be made to schedule the visit in this window, however if the COVID-19 pandemic situation affects the ability to achieve this then, for those COVID-19 specific instances, the visit window can be expanded to ±28 days.
- Early Withdrawal Visit 1-4 weeks after last dose for participants that withdraw from the study.
- c. To be conducted prior to clinical assessments.
- d. Survival assessment at Week 52 for participants who withdraw before Week 52.
- e. Serum pregnancy test at Screening; Urine pregnancy test at all other visits, including pregnancy test 16 weeks after last dose of belimumab. The pregnancy test 16 weeks after the last dose of belimumab may be done at home, with the results reported by telephone call to the clinic. See Section 9 for pregnancy test requirements.
- f. At Week 4 and Week 6 pre-rituximab/ rituximab-placebo dose.
- g. At Week 4 post-rituximab/rituximab-placebo dose and at Week 6 pre- and post- rituximab/rituximab-placebo dose.
- h. At Week 32 only.
- i. The first dose of belimumab will be administered at the clinic and the subject needs to stay for 3 hours post dose for observation.
- j. Premedication administration will be given 30 minutes prior to each Rituximab / rituximab-placebo dose and the subject needs to stay in clinic for 1 hour post dose for observation (i.e., Clinical monitoring including vital signs). If the subject misses the Week 4 dosing visit and dosing will take place during an unscheduled visit, the first dose of rituximab should be scheduled no later than 7 days after Week 4. The second dose of rituximab must be administered at least 2 weeks but not more than 3 weeks after the first rituximab dose.

 NOTE: Contact Medical Monitor if the date of a) first dose is more than 1 week past week 4, and b) if the date of the second dose of rituximab would exceed 3 weeks after the first dose. During unscheduled visits, procedures for Immunogenicity and PK will follow the schedule for Week 4 and Week 6.
- k. It is recommended that the steroid taper be initiated on Week 12 to reach the target prednisone equivalent of ≤5 mg/day at Week 26, but the taper schedule is at the discretion of the investigator.

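### The 10-day allowance in SAP 6.6 is shorter than the permitted visit window, so some participants who took their last planned belimumab dose on schedule are plotted as having discontinued

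*SAP*

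**What the plan says.** SAP Section 6.6 defines time to belimumab discontinuation. For every arm in Year 1, and for Arms A and B over Years 1 and 2, the event condition is "If the last dose of belimumab+10 days is prior to the Week 52 visit date". For Arm C over both years it is "If the last dose of belimumab + 10 days is prior to the Week 104 visit date". The visit date is the observed one. If there was no visit it is "predicted as day1+364 for subjects who do not have a Week 52 visit" or "predicted as day1+728 for subjects who do not have a Week 104 visit". An event is dated "at the earliest non-missing date of (last dose date +7, date of death, withdrawal date, LTFU date". Anyone else is censored at the observed or predicted visit, or at an earlier death, withdrawal or loss to follow-up. Participants who received every planned dose are not exempted.

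The Protocol Synopsis sets dosing as "weekly (i.e., every 7 days ±1 day) through Week 51 for Arms A and B, and through Week 103 for Arm C". Footnote a to the schedule-of-activities tables, for Year 1 and for Arm C in Year 2, says that "a study visit time window ± 7 days is acceptable", and widens this to 28 days either way where COVID-19 is the cause.

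The second SAP addendum corrects the neighbouring Section 6.5 (which doses belong to which year) but leaves 6.6 alone. It keeps Figure 21.02 and a table with the same title, Table 21.06.

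**The concern.** No dose is due after Week 51 in Arms A and B, or after Week 103 in Arm C. From then on, a later visit lengthens the interval from last dose to visit without any dose having been missed. A rule that reads this interval as stopping early therefore turns visit scheduling into discontinuation.

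The false event is dated 7 days after the last dose. For an on-schedule participant that is exactly the scheduled Week 52 or Week 104 date, so planned completion is shown as premature stopping. In the Year 1 figure the step can appear only in Arms A and B, because Arm C is still dosing weekly at Week 52. A reader could take it for poorer persistence in the blinded arms than in the reference arm. The rule also treats like cases differently: a participant with the same dosing record but no Week 52 visit is censored.

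**Working it through.** **Inputs.** Study Day 1 is the first dose (SAP 5.2). The last planned dose is at Week 51 or Week 103, with a tolerance of 1 day either way (Protocol Synopsis). The visit window is ±7 days, or ±28 for COVID-19 instances (Protocol Section 2). The allowance is 10 days (SAP 6.6).

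**The plan's own figures.** Week w falls on Day 7w + 1. For Week 52, 52 × 7 = 364, which gives day1+364, or Day 365. For Week 104, 104 × 7 = 728, which gives day1+728, or Day 729. Both agree with SAP 6.6 and with the targets in SAP Appendix 3.

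**Last planned dose.** Arms A and B: 51 × 7 + 1 = Day 358. Arm C: 103 × 7 + 1 = Day 722.

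**Test.** A participant is an event if last dose + 10 is earlier than the visit day. The limits are 358 + 10 = Day 368 and 722 + 10 = Day 732.

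| Setting | Visit window | Visit days that give an event | Window days affected | Event dated |
|---|---|---|---|---|
| A/B, Week 52, ±7 | 358-372 | 369-372 | 4 of 15 (27%) | 358 + 7 = 365 |
| A/B, Week 52, ±28 | 337-393 | 369-393 | 25 of 57 (44%) | 365 |
| C, Week 104, ±7 | 722-736 | 733-736 | 4 of 15 (27%) | 722 + 7 = 729 |
| C, Week 104, ±28 | 701-757 | 733-757 | 25 of 57 (44%) | 729 |

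**Dosing tolerance.** A last dose 1 day early moves the first affected Week 52 visit to Day 368 (5 of 15, or 26 of 57). One day late moves it to Day 370 (3 of 15, or 24 of 57). The ranges are 20-33% and 42-46% of window days.

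**Allowance needed.** To cover the whole window after an on-schedule dose takes 372 − 358 = 14 days for ±7 and 393 − 358 = 35 days for ±28, against the 10 stated.

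**Comparison cases.**
- No Week 52 visit: Day 368 is not before Day 365, so the participant is censored.
- Arm C at Week 52: with doses 7 or 8 days apart and continuing, the interval from last dose to visit never exceeds 10 days, so no visit day in either window gives a false event.
- A late Year 1 dose taken on Day 365: 365 + 10 = 375, so no visit in the ±7 window is affected, although Days 376-393 of the ±28 window still are.

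**The case against.** The strongest reply is that little depends on this. Section 6.6 belongs to the study population analyses and tags two Kaplan-Meier figures and some listings. The step in Arms A and B falls at about Day 365, where F21.02 truncates those curves anyway. The rule is identical in A and B, so it builds in no difference between them. All of this stands, and it keeps the point small.

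The day counts also need care. It is tempting to read 27% and 44% as shares of participants. That would require visits spread evenly over the window, which nothing in the documents supports: the protocol asks sites to make every effort to stay within 7 days and reserves 28 for COVID-19 instances. Nor is everyone seen on Day 369 or later affected. The 1-day dosing tolerance shifts the limit, and SAP 6.5 expects that some participants in Arms A and B will take late Year 1 doses, which can remove the effect.

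Table 21.06 shares the figure's title, but Section 6.6 does not tag it. Section 6.2 describes the corresponding table in the main SAP (T21.07) as cumulative discontinuations by visit. Its use of this derivation is plausible but not stated.

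Other definitions would treat the same participant as on treatment: the *Ongoing on study treatment at Week 52* population (SAP 4), which tolerates gaps of up to 28 days, and the on-treatment period to last dose + 28 days (SAP 5.12). These serve different purposes, so the mismatch is not in itself a contradiction.

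None of this removes the defect. Applied exactly as written, the rule produces false events, and no other section corrects it.

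**Conclusion.** The point holds as a derivation flaw in descriptive displays. A participant whose last planned dose was on schedule is recorded as discontinued when the Week 52 visit (Arms A and B) or the Week 104 visit (Arm C, Years 1 and 2) is 4 or more days late but still inside the permitted window. This affects 4 of 15 window days, or 25 of 57 under the COVID-19 extension. The number of participants cannot be given without the visit dates. The visible result is a false step at the end of planned treatment in F11.02 and F21.02, and in Table 21.06 if it uses the same derivation. In the Year 1 figure it falls on Arms A and B only.

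A reader might infer that efficacy results are compromised. The documents do not support that. Discontinuation of study drug is expressly not a component of the primary endpoint (SAP 7.1.1) or of the first major secondary endpoint (SAP 7.2.1), and the second uses the primary definition at Week 104 (SAP 7.3.1). The Composite and Hybrid On Treatment estimands do use drug discontinuation, but nothing says that they take the flag from Section 6.6.

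**What to change.** Amend Section 6.6 for two settings only: Arms A and B at Week 52, and Arm C at Week 104 in the Year 1 and 2 display. Class a participant as discontinued only if last dose + 10 days is before the earlier of the observed visit date and the scheduled date (day1+364 or day1+728). Otherwise censor at that earlier date, or at an earlier death, withdrawal or loss to follow-up.

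On-schedule completers are then censored (368 ≥ 365; 732 ≥ 729), as are those whose last dose was 1 day early (367 ≥ 365; 731 ≥ 729). Participants who stopped well before the end remain events.

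Keep the observed-visit comparison for Arm C in the Year 1 display. Capping it at Day 365 would lose real stops: an Arm C participant whose last dose was on Day 358 and who is seen on Day 372 has stopped and is correctly an event now (368 < 372), but would be censored under the cap (368 ≥ 365).

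State whether Table 21.06 uses this derivation. The cost is one SAP sentence, a small programming change, and a check of F11.02 for events at about Days 364-366 in Arms A and B.

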7. EFFICACY ANALYSES

The primary objective of the study is to demonstrate superiority (improvement in response rate) of co-administration of belimumab plus rituximab (Arm B: Combination) over belimumab monotherapy (Arm A: Control), when comparing the primary efficacy endpoint at Week 52 in subjects with SLE.

An exploratory summary of Arm B (Combination) vs Arm C (Reference) will also be shown.

SLEDAI-2K score has been measured by both the principal investigator (PI) and the independent blinded assessor (IBA). The key differences between these assessments is the frequency of assessment and awareness of the treatment allocation for Arm C:

- The principal investigator conducts a SLEDAI-2K assessment every 4 weeks in Year 1 (at least every 8 weeks in Year 2), whereas the independent blinded assessor conducts a SLEDAI-2K assessment at a reduced set of key time points (weeks baseline, 12, 26, 40, 52, 64, 80, and 104).
- The principal investigator knows which of their subjects are randomised to treatment arm C, but does not know if their remaining subjects are randomised to arm A or arm B. The independent blinded assessor however is not aware of any MITT population subject's treatment randomisation (Section 4).

Due to the level of blinding the primary and major secondary efficacy endpoints will be conducted using the independent blinded assessors' SLEDAI-2K assessment. Note however the PI assessment of SLEDAI-2K at baseline, is used as the baseline covariate in all adjusted analysis (the baseline SLEDAI-2K assessment is conducted prior to randomisation).

The other secondary endpoints analysis utilises the greater visit frequency of the principal investigator assessment. This is particularly pertinent for differentiating between treatments when considering time to response or duration of response. In by visit summaries, it also allows for the assessment of fluctuating response.

The primary and major secondary efficacy endpoints are repeated using the principal investigator assessment.

Details of the planned displays are provided in Section 15.11 and are based on GSK data standards and statistical principles. Listings of all key efficacy endpoints will be provided [L12.01 – L12.02, and L22.01-L22.02].

7.1. Primary Efficacy Analyses

7.1.1. Endpoint / Variables

The protocol defined primary endpoint is the proportion of participants with a state of disease control defined as a SLEDAI-2K score ≤ 2 (IBA), achieved without immunosuppressants and with corticosteroids at a prednisone equivalent dose of ≤ 5 mg/day at Week 52 (Protocol Section 4).

The protocol Section 10.4.1 Efficacy analysis then clarifies that:

For participants who withdraw prematurely from study treatment and for who subsequent collection of data is not possible, it will be assumed for the primary analysis that they are treatment failures. A dropout/treatment failure = non-responder (DO/TF=NR) analysis will be used .

Hence when adopting the ICH Estimands and Sensitivity Analysis in Clinical Trials E9 R1 addendum terminology, this endpoint is defined as:

| Disease Control |
|--|
| 
Responder:
 
 • SLEDAI-2K score ≤ 2 (IBA); and • Not a TF at the current or any prior visit (TF includes consideration of corticosteroids and immunosuppressants); and • Did not withdraw from the study prior to the visit 
Non-Responder:
 
 • SLEDAI-2K score > 2 (IBA); or • TF at the current or any prior visit (TF includes consideration of corticosteroids and immunosuppressants); or • Withdrew from the study prior to visit (which includes study withdrawal, lost to follow-up and death) |
| 
The derivation of SLEDAI-2K score is provided in Section 15.6.3, treatment failures are defined in Section 15.6.15. and withdrawal from the study prior to Week 52 in Section 5.9.
 |
| 
Note: Discontinuation of study investigational product (belimumab or rituximab) is NOT a component of this endpoint, subjects who discontinue investigational product will only be non-responders if they also meet one of the criteria above.
 |

Note this clarification of notation does not change the protocol-specified primary analysis.

The analysis of the primary endpoint of Arm A vs Arm B will use data from treatment Arms A, and B only.

An exploratory analysis of the relative performance of Arm B vs. Arm C will also be conducted, using data from Arms B and C only.

7.1.2. Summary Measure

The odds ratio at Week 52 between Arm B (Combination) vs Arm A (Control).

7.1.3. Population of Interest

The primary efficacy analyses will be based on the Modified Intent-To-Treat population, unless otherwise specified.

7.1.4. Strategy for Intercurrent (Post-Randomization) Events

There are 5 potential types of intercurrent events considered for this study:

- Treatment Failure
- Study Withdrawal
- Lost to Follow-up
- Death
- Investigational Product (IP) Discontinuation .

Whilst study withdrawal and lost to follow-up (LTFU) are not true intercurrent events per ICH Estimands and Sensitivity Analysis in Clinical Trials E9 R1 addendum terminology; they are included in the reporting here to allow for backward compatibility to the study Protocol (see Section [7.1.1](#)).

Four intercurrent event strategies are employed:

- Hybrid strategy considers all data while the subject is continuing in the study irrespective of IP discontinuation. Treatment failure and study withdrawal (including LTFU and death) are components of the endpoint definition. Subjects who discontinue investigational product (belimumab) are encouraged to continue in the study.
- Composite strategy considers data collected only while the subject is continuing to receive study treatment. Treatment failure and study withdrawal (including LTFU and death), and IP discontinuation are components of the endpoint definition.
- Hybrid on treatment strategy considers data collected only while the subject is receiving study treatment. Treatment failure and study withdrawal (including LTFU and death), are components of the endpoint definition. IP discontinuation are excluded (unless already experienced treatment failure).
- Treatment Policy strategy considers all data while the subject is continuing in the study irrespective of IP discontinuation or Treatment Failure. Study withdrawal (including LTFU and death), are components of the endpoint definition

The main estimand of this endpoint, is a Hybrid strategy, subjects who discontinue investigational product will continue in the study, assessments after treatment discontinuation will be included in the main estimand. Subjects who are a treatment failure or withdraw from the study will be a non-responder for this estimand.

An analysis of 3 supportive estimands will also be conducted using the alternative intercurrent event strategies, namely:

- Composite,
This will include IP discontinuation as an intercurrent event resulting in the subject being a non-responder.
- Hybrid On treatment,
This will only include subjects whilst they are on treatment, or if they have met the definition of a non-responder prior to discontinuing treatment.
- Treatment Policy,
Assessments after IP discontinuation and assessments after Treatment Failure will be included. Subjects who withdraw from the study will be non-responders.

The impact of the different IP discontinuation components of the endpoint for the Hybrid and composite estimands is summarised by considering 6 hypothetical scenarios:

Table 2 Scenarios for the components of the Hybrid and composite endpoint

| Example Subject | SLEDAI-2K score at Week 52 | Study Withdrawal(including Lost to Follow-up, or Death) prior to Week 52 | Treatment Failure prior to Week 52 | IP Discontinuation prior to Week 52 | Main Estimand Hybrid | Supplemental Estimand Composite |
|-----------------|--|--|------------------------------------|-------------------------------------|----------------------|---------------------------------|
| 1 | >2 | N | N or Y | N or Y | NR | NR |
| 2 | <=2 | N | N | N | R | R |
| 3 | <=2 | N | N | Y | R | NR |
| 4 | <=2 | N | Y | N or Y | NR | NR |
| 5 | Incomplete* or entirely missing | N | N or Y | N or Y | NR | NR |
| 6 | Missing - does not exist due to study withdrawal | Y | N or Y | Y | NR | NR |

R = Responder; NR = Non-Responder

*Incomplete: does not include partial scores where it is possible to determine that the total score must be >2, or that the maximum possible score (assuming worst case for missing data) is <=2 (see Section 15.6.4 Partial but informative SLEDAI-2K score).

A full breakdown of scenarios ‘by subject type’ and including Hybrid On Treatment and Treatment Policy is provided in Section 15.6.4

7.1.5. Statistical Analyses / Methods

7.1.5.1. Statistical Methodology Specification

| |
|---|
| Endpoint / Variables |
| 
 The proportion of participants with a state of disease control defined as a SLEDAI-2K score ≤ 2 (IBA), achieved without treatment failure or study withdrawal |
| Derivation |
| 
 Derivation of the endpoint for Arms A, B and C is provided in Section 15 |
| Model Specification |
| 
 Logistic regression model. Terms in the model: 
 Dependent: response (yes/no) Categorical: treatment group, baseline SLEDAI-2K score (≤ 9 vs. ≥ 10), baseline immunosuppressant use (use vs. non-use), and baseline corticosteroid dose (prednisone equivalent ≤ 10 mg/day vs. > 10 mg/day). |
| Model Checking & Diagnostics |
| 
 If any factor fails to converge it will be removed from the logistic model. If the logistic model fails to converge, e.g., due to a small number of responders, the primary endpoint will be analyzed using a Fishers exact test. If the model diagnostics raise questions about the validity of the analysis additional non-parametric analysis will also be conducted. |
| Model Results Presentation |
| 
 The table [T12.01] will display: 
 the number, percentage, SE of percentage, and the 95% CI for the percentage of subjects achieving a response by treatment group, the observed difference in percentage of responders for the comparison of Arm B vs Arm A; and Arm B vs Arm C, the stratified (baseline SLEDAI-2K score, baseline immunosuppressant use, baseline corticosteroid dose) Cochran-Mantel-Haenszel treatment difference and 95% confidence interval (CI) for the comparison of Arm B vs Arm A; and Arm B vs Arm C. the odds ratio and 95% confidence interval (CI) for the comparison of Arm B vs Arm A; and Arm B vs Arm C. the p-value for the odds ratio the treatment difference for Arm B vs Arm A. A table [T12.02]. showing the details from the logistic regression will also be presented; including: 
 the parameter estimate and standard error for each of the terms in the model the odds ratio and 95% CI and p-value for each covariate in the model the parameter estimate, standard error, odds ratio, 95% CI and p-value for the comparison of Arm B vs Arm A |

- the parameter estimate, standard error, odds ratio, and 95% CI for the comparison of Arm B vs Arm C
- the odds ratio and 95% CI for the comparison of Arm A vs Arm C
- The proportion of participants with a state of disease control at Week 52 will be displayed in a point estimate +/- SE figure, by treatment group [F12.01].

Subgroup Analyses

The comparison of the primary efficacy endpoint between Arm B vs. Arm A will be performed by the following subgroups [F12.02]:

- Age (<65 years vs. ≥65 years) [T12.16].
- Race (Black vs. Non-Black) [T12.17].
- Gender (Male vs. Female) [T12.18]
- Baseline SLEDAI-2K score (≤ 9 vs. ≥ 10) [T12.19].
- Baseline immunosuppressant use (use vs. non-use) [T12.20].
- Baseline corticosteroid dose (prednisone equivalent ≤10 mg/day vs. >10 mg/day) [T12.21].
- Baseline C3/C4 levels & anti-dsDNA (At least one C3/C4 low & anti-dsDNA ≥ 30 IU/mL vs. NOT (At least one C3/C4 low & anti-dsDNA ≥ 30 IU/mL)) [T12.24].
- BLYS Protein at baseline (≥ 75th Percentile vs. < 75th Percentile) [T12.25].
- Country Region (USA/Canada vs. Europe vs. Rest of World) [T12.26].
- Baseline complement level (At least one low C3/C4 vs. No low C3/C4) [T12.22].
- Anti-dsDNA (<30 IU/mL vs. ≥30 IU/mL) [T12.23]
- RNA Interferon Signature at baseline (Low vs. High) [T22.34] (note this assessment of subgroups for the primary endpoint will be reported at the end of the study).

Each of the subgroups will be analysed separately using a logistic regression model with adjustment for the stratification factors, using the Intercurrent event strategy: Hybrid . If the model fails to converge the relevant stratification factor(s) will be removed from the model.

To further assess each subgroup, the interaction between treatment and the subgroup will be tested by fitting a logistic regression model to the data (all subgroups combined). The model, will include the stratification factors, the variable for the subgroup, and the interaction term between treatment group and the subgroup. The summary table will include the p-value for the interaction that tests the of stability of Arm B vs Arm A over the 2 (or more) levels of the subgroup. If the logistic model fails to converge then the interaction p-value will not be presented.

Supportive Analyses

- The disposition of the primary endpoint, detailing the reasons why a subject was a non-responder will be summarized (n,%) [T12.03, T12.04].
- The components of the primary endpoint will be summarized [T12.05]. i.e. proportion of participants with:
 - SLEDAI 2K-score ≤2 (IBA)
 - Treatment failure due to corticosteroid use
 - Treatment failure due to immunosuppressant use
 - Treatment failure due to anti-malarial, NSAID, Aspirin or other prohibited medication use
 - Study withdrawal
- The table will include

- the number, percentage, SE of percentage, and the 95% CI for the percentage of subjects achieving a response by treatment group
- the odds ratio and 95% confidence interval (CI) for the comparison of Arm B vs Arm A; and Arm B vs Arm C.
- the p-value for the odds ratio the treatment difference for Arm B vs Arm A
- The primary efficacy analysis at Week 52 will be repeated to assess the robustness of the primary efficacy results:
 - ITT population –Including subjects where the independent blinded assessor was potentially unblinded at Week 52 . Intercurrent event strategy: Hybrid [T12.06].
 - Unadjusted for covariates. the only independent variable in the model will be treatment group. Intercurrent event strategy: Hybrid [T12.07].
 - Composite. Intercurrent event strategy: Composite [T12.08].
 - Hybrid On treatment. Intercurrent event strategy: Hybrid On Treatment [T12.10].
 - Treatment Policy. Intercurrent event strategy: Treatment Policy [12.11].
 - Per Protocol population. Intercurrent event strategy: Hybrid[T12.09].
 - Ongoing on study treatment at Week 52 population. Intercurrent event strategy: Hybrid on Treatment [T12.12].
- A supportive analysis that considers all the data from Arms A, B, and C in the same model will also be conducted. Estimates of the treatment effect will be made for comparison of Arms A vs B and Arms B vs C. Intercurrent event strategy: Hybrid (T12.13)
- Two tipping point analyses may be performed if there is a significant treatment difference, including all recorded data up to the time of study withdrawal, and using differing assumptions regarding data missing following study withdrawal (Section 7.1.6). Intercurrent event strategy: Hybrid [T12.14, F12.03]. Intercurrent event strategy: Treatment Policy [T12.15, F12.04].

